7.4.6. Bone Lesions

Findings of bone scans will be assessed using the Soloway Scale (0 = No lesions, 1 = 1-5 lesions, 2 = 6-20 lesions, 3 = ≥ 21 lesions but not a superscan, 4 = superscan). The Soloway Scores by visit will be summarized using descriptive statistics. The number of subjects with bone lesions only (no measurable soft tissue lesions) will also be summarized as frequency distributions at each visit. A shift table of Soloway Scores by study visit against the baseline scores for Months 3, 6, 9, and 12 will be prepared. Soloway Scores for each subject will also be listed.

7.4.7. Tumor Markers

Tumor markers (e.g., serum chromogranin A) will be assessed as stated in the Schedule of Procedures. For each individual tumor marker, results will be categorized per the response criteria in the following table. If the tumor marker value prior to dosing is less than 1.5 times the upper limit of normal for the respective marker, it will not be included in this analysis.

Response	Criteria for Response
Complete Response (CR)*	Normalized, at or below upper limit of normal (ULN)
Partial Response (PR)*	$\geq 50\%$ decrease in baseline value but above the ULN
Stable Disease (SD)	Any response other than CR, PR or PD
Progressive Disease (PD)	$\geq 50\%$ increase in baseline value
Not Evaluable (NE)	Below 1.5 X ULN at baseline, or baseline missing

* To be assigned a status of CR or PR changes in tumor marker measurements must be confirmed by repeat assessments

For the Full Analysis Set, summary tables for confirmed tumor marker response, for each marker, will be prepared by visit window and all measurements of tumor markers will be listed. A confirmed response will require that the subsequent tumor marker assessment be identical or better compared with the previous response assessment.

Subjects will be evaluated to determine the best confirmed response for each tumor marker that is ≥ 1.5 x ULN at baseline. A listing of the best confirmed response for each tumor marker, at what time it becomes apparent, and the duration of any positive response (CR or PR) will be generated. The response is considered to be ended when the tumor marker response becomes confirmed at SD or PD.

Each subject will also be evaluated to determine if that subject is an overall tumor marker responder. An overall responder will be a subject who achieves a best confirmed response of either CR or PR at some time point, on each of the plasma and urine tumor markers that were abnormal at baseline, with the exception of urine VMA.

An additional analysis will be performed where the tumor marker response will be summarized for the dominant tumor marker for each subject. The dominant tumor marker will be identified prior to database lock by the Medical Monitor.

Analysis will determine if there is an association between achieving an overall best tumor marker response of CR or PR with achieving primary endpoint responder status based on the reduction in antihypertensive medications.

Additional correlations between tumor marker responses and other endpoints may be performed as exploratory analyses.

Correlations using the tumor marker response for each tumor marker will be performed at the 3, 6, 9, and 12 month visit windows. These correlations are listed below.

- Tumor marker responses among the different tumor markers.
- Tumor marker response and overall unmodified RECIST response will also be performed: tumor response will be coded as 1 (CR), 2 (PR), 3 (SD), and 4 (PD).
- An additional analysis, tabulating the best overall confirmed tumor marker response and best overall RECIST response through 12 months post first therapeutic dose, will also be performed. For this analysis, the best overall confirmed tumor marker response and the best overall RECIST tumor response will be treated as binary variables, with responses of CR and PR combined as a positive response and SD and PD combined as a negative response.

Spearman correlation coefficients will be reported for all correlations, and Fisher's exact test will be used for binary response comparisons.

For the purposes of tabulations, tumor marker evaluations where there is a comment that the value is above or below the clinical reportable range will be set to the upper or lower limit of normal as applicable.

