7.4 Biomarkers for Pheochromocytoma and Paraganglioma

Pheochromocytomas and paragangliomas are rare tumors of chromaffin cells with pheochromocytomas arising from tissue of the adrenal medulla and paragangliomas located at extra-adrenal sites along the sympathetic or parasympathetic chain.¹⁹ Pheochromocytoma and paragangliomas can synthesize, store and secrete catecholamines, and more rarely dopamine, causing a variety of clinical symptoms.^{20,21} Even if they do not secrete hormones, pheochromocytomas synthesize catecholamines at increased rates that may be up to 27 times the synthetic rates of the normal adrenal medulla. Catecholamines are produced in quantities that exceed the vesicular storage capacity and accumulate in the cytoplasm of the tumor cells. Here they are subject to intracellular metabolism, and the excess catecholamines and metabolites diffuse out of the tumor cells into the circulation.²²

Pheochromocytoma cells contain catechol-O-methyltransferase and therefore metabolize catecholamines locally releasing free metanephrines and other metabolites. This fact, combined with the usually low rates of extraneuronal catechol-O-methylation and the relatively large contribution of adrenal medullary cells to normally low plasma levels of free metanephrines, provides the extraordinary sensitivity of these measurements for detecting the presence of pheochromocytoma tumor cells. That is, the plasma level of these hormones is amplified by intratumoral formation of free metanephrines.^{23,24} Secretion of catecholamines and other bioactive hormones into the plasma is episodic, and measurement of the parent compounds is therefore variable. However, metanephrines, the metabolites of catecholamines, are produced continuously within the pheochromocytoma tumor cells independent of catecholamine release,²¹ and the production of O-methylated metabolites is independent of the highly variable release of catecholamines.²⁵

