13.3.2.2.2 Tumor Marker Response Proportion

Tumor markers will be assessed as stated in the Schedule of Procedures (Appendix VII). For all tumor markers, a significant increase in test value is indicative of progression, and a significant decrease is indicative of a response.

For each individual tumor marker, response criteria are defined as follows:

Complete Response (CR)	normalized, at or below ULN
Partial Response (PR)	\geq 50% decrease in baseline value
Stable Disease (SD)	any response other than CR, PR or PD
Progressive Disease (PD)	\geq 50% increase in baseline value

To be assigned a status of PR or CR, changes in tumor measurements must be confirmed by repeat assessments that should be performed no less than 4 weeks after the criteria for response are first met.

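### SAP 7.4.7 has one tumor marker confirmation rule, which read literally runs the wrong way for loss of response and also leaves CR followed by PR unconfirmed

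*SAP*

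**What the plan says.** SAP 7.4.7 sorts each marker value into CR, PR, SD, PD or not evaluable. A table footnote states: "To be assigned a status of CR or PR changes in tumor marker measurements must be confirmed by repeat assessments". SD and PD carry no such mark. The operational rule follows in the text: "A confirmed response will require that the subsequent tumor marker assessment be identical or better compared with the previous response assessment". The end of a response is then defined: "The response is considered to be ended when the tumor marker response becomes confirmed at SD or PD". No other sentence says how SD or PD becomes confirmed.

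The section uses the word response for every category. SD, for instance, is "Any response other than CR, PR or PD", and benefit has to be singled out with a qualifier: a listing of "the duration of any positive response (CR or PR) will be generated".

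Protocol 13.3.2.2.2 covers confirmation of PR and CR only, by a second assessment with a four-week minimum gap. It has no rule for the end of a response. On variability, Protocol 7.4 says: "Secretion of catecholamines and other bioactive hormones into the plasma is episodic, and measurement of the parent compounds is therefore variable".

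**The concern.** A requirement that the next value be the same or better is a sensible test of whether a benefit is real. As a test of whether a benefit has been lost it points the wrong way: recovery confirms the loss and further worsening does not. If a programmer applies the only stated rule to SD and PD, one fluctuating sample can close a response that is still present, and the listed duration of CR or PR is cut short.

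The rule also has a gap when a response is being established. A subject who normalizes and then drifts slightly above the upper limit of normal (ULN), while still at least 50% below baseline, moves from CR to PR. PR is worse than CR, so the CR is not confirmed. If the next value is SD, the PR is not confirmed either. This affects best confirmed response, and through it overall marker responder status and the binary tabulation against RECIST response.

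**Working it through.** **Order of categories.** SAP 7.4.7 codes RECIST response 1 to 4 in the order CR, PR, SD, PD. I assume that this order also defines better for markers.

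**Loss of response.** The table takes a subject already in confirmed CR or PR. The literal rule counts SD or PD as confirmed when the next category is the same or better. The alternative requires two consecutive values that are each SD or PD.

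| Next values | Literal rule | Two consecutive SD/PD |
|---|---|---|
| SD, CR | ends at SD | continues |
| SD, PR | ends at SD | continues |
| SD, SD | ends at first SD | ends at first SD |
| SD, PD, any later value | ends at PD | ends at SD |
| SD, PD (last sample) | does not end | ends at SD |
| PD, CR or PR | ends at PD | continues |
| PD, SD | ends at PD | ends at PD |
| PD, PD | ends at first PD | ends at first PD |

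PD is the worst category, so any later value confirms it. SD followed by PD therefore ends the response one visit late, unless no later sample exists. One visit is 2 weeks during Weeks 2–24 and about a month during Months 7–12. In follow-up, where the SAP Appendix 1 windows are 6 months apart, it is about 6 months.

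**Establishing response.** In CR, PR, SD, neither CR nor PR is followed by the same or a better category, so nothing is confirmed. PR requires a value above ULN and at most half of baseline, so baseline must exceed 2 × ULN. A CR value (at or below ULN) is then also below half of baseline. Both values were therefore at least 50% below baseline.

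**Illustration of size.** The documents give no figure to reproduce. The schedule has 12 samples in Weeks 2–24 and 6 in Months 7–12, 18 in all. If two establish the response, 16 remain. Assume a truly sustained response and an independent chance p of an SD reading at each sample, with no PD.

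- Literal rule: an SD at any of the first 15 samples is followed by the same or a better category, so P(ended) = 1 − (1 − p)^15.
  - p = 0.05: 1 − 0.4633 = 0.537
  - p = 0.10: 1 − 0.2059 = 0.794
  - p = 0.20: 1 − 0.0352 = 0.965
- Two consecutive SD/PD: let a be the probability of no end so far with the last value not SD, and b the probability of no end so far with the last value SD. Start at a = 1, b = 0. At each sample, new a = (1 − p)(a + b) and new b = p·a. After 16 samples P(ended) = 1 − a − b.
  - p = 0.05: 1 − 0.9186 − 0.0460 = 0.035
  - p = 0.10: 1 − 0.7905 − 0.0798 = 0.130
  - p = 0.20: 1 − 0.4882 − 0.1011 = 0.411

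**The case against.** The strongest reply is that the SAP never says the rule governs SD and PD. The footnote asks for confirmation of CR and PR only, as does the protocol, and confirmed at SD or PD can naturally mean that a repeat sample is again SD or PD. This stands in part: the backward result follows from one reading. On the other reading the end-of-response rule is undefined, and two programmers could derive different durations. Either way the section needs a sentence.

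The second reply is that the consequence is small. Marker-response duration appears in a listing only. No planned table or figure in SAP Section 11 reports it, and all marker values are listed, so duration could be re-derived. This stands for the end-of-response rule. It does not answer the CR, PR, SD gap, which feeds summarized results.

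The third reply concerns noise. The protocol's remark on episodic secretion is about the parent catecholamines. Protocol 7.4 also says that metanephrines are produced continuously and that chromogranin A and metanephrines track tumor mass. Above 2 × ULN at baseline, a small rise from CR gives PR rather than SD. This stands: the values of p are assumptions and may be too high for some markers. In the other direction, a baseline from 1.5 to 2 × ULN leaves no room for PR, so a normalized marker that reads just above ULN goes straight to SD.

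A reader might also infer that steady worsening prolongs a response indefinitely. The documents do not support that. The delay is one visit unless PD is the last value. That case can arise, because progressive disease is a discontinuation criterion (Protocol 9.7) and discontinued subjects have no further marker tests (Protocol 9.8).

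**Conclusion.** The point holds in a limited form. SAP 7.4.7 supplies one confirmation rule, which suits CR and PR. Applied literally to SD and PD it lets an isolated dip end a response and delays, or at the last sample misses, the end when SD is followed by PD. The effect is confined to listed duration. The illustration of 54%, 79% and 96% against 4%, 13% and 41% rests on the literal reading, on independent dips to SD only, and on values of p that the documents do not supply.

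The CR, PR, SD gap does not depend on that reading, because it concerns the categories the rule plainly covers. It can lower best confirmed response where the marker has no other confirmed CR or PR. Overall marker responder status needs CR or PR on every plasma and urine marker abnormal at baseline except urine VMA, so one marker missed in this way is enough to change it. I have not put a frequency on this.

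Two stronger conclusions are not supported. The documents do not show that listed durations mainly reflect noise. Nor is the primary endpoint touched, since it is derived from antihypertensive use.

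**What to change.** In SAP 7.4.7:

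1. Limit the identical-or-better rule to confirming CR and PR.
2. State that CR followed by PR confirms PR.
3. State that a response ends at the first of two consecutive assessments that are each SD or PD, in any order.
4. Treat a single SD or PD at the last available assessment as unconfirmed, censor the duration at that date and flag it in the listing.

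Item 4 matters. Counting a lone final SD as the end would let one unconfirmed dip close a response again. In the illustration it would raise the 4%, 13% and 41% to 1 − a = 8.1%, 20.9% and 51.2%.

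The same edit could reconcile the SAP's next-sample rule with the protocol's four-week minimum for CR and PR.

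The cost is a few sentences and minor reprogramming. Some listed durations will become longer, and where SD is followed by PD the end moves back to the SD visit.

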Use of antihypertensive medication will be measured through standard, ongoing reporting of concomitant medications throughout the study until completion of the follow-up period. Tumors will be measured by computed tomography (CT) with contrast or magnetic resonance (MR) imaging at baseline and at 3, 6, 9 and 12 months after the first Therapeutic Dose. Obtaining renal volume for each kidney is required at baseline. A bone scan will be performed at Screening/baseline and if probable metastatic disease is observed or suspected, additional bone scans will be performed at Month 3, 6, 9, 12. Overall tumor response at 3, 6, 9 and 12 months per RECIST criteria will be assessed centrally by independent, blinded readers. FDG scans may also be performed at baseline and 3, 6, 9, and 12 months to assess viable tumor tissue. Tumor markers [serum chromogranin A, plasma free metanephrines and normetanephrines, 24 hour urinary vanillylmandelic acid (VMA), plasma catecholamines (dopamine, epinephrine and norepinephrine), 24 hour urinary catecholamines (dopamine, epinephrine and norepinephrine) and urinary metanephrines and normetanephrines] will be evaluated by a central laboratory. Testing for tumor markers will occur at baseline, every two weeks for the first 24 weeks after the first Therapeutic Dose starting at Week 2, and monthly during months 7-12. Renal function will be assessed through either creatinine clearance or Glomerular Filtration Rate (GFR) at baseline and at the Months 6 and 12 Efficacy Visits. Evaluation of thyroid function (T3, T4 and TSH) and clinical evaluation of possible dry mouth will be performed at the 12 month Efficacy Visit. Use and dose of antihypertensive, pain and other medication required for tumor associated signs and symptoms will be recorded on an on-going basis throughout the study until completion of the follow-up period. Subject-reported Quality of Life measurements will be obtained through the EORTC QLQ-C30 v3 and the NIH Quality of Life and Symptoms Questionnaire for Pheochromocytoma and Paraganglioma. The frequency of the procedures is summarized in the Schedule of Procedures (Appendix VII). Subject may undergo additional assessments as warranted (for example, to confirm tumor response) at unscheduled visits.

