11.5.10 Tumor Markers

Each subject will receive a baseline evaluation of tumor markers (serum chromogranin A, plasma free metanephrines and normetanephrines), 24 hour urinary vanillylmandelic acid (VMA), plasma catecholamines (dopamine, epinephrine and norepinephrine), 24 hour urinary catecholamines (dopamine, epinephrine and norepinephrine) and urinary metanephrines and normetanephrines, during the screening/ baseline period. Additional laboratory testing for tumor markers will include measurements every two weeks during weeks 2-24, monthly during Months 7 through 12 following the first therapeutic Ultratrace iobenguane I 131 infusion and during the

long-term follow-up through assessments provided as institutional standard of care (Section 11.5.17). All tumor markers will be evaluated by a central laboratory.

Although not a requirement, it is suggested that patients refrain from smoking or eating for at least 4 hours prior to blood draws for tumor markers to ensure reliable test measurements Subjects should sit quietly for 10-20 minutes before the phlebotomy. For dietary/medication considerations before tumor marker collection please refer to the guidelines provided in the Study Manual Binder.

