APPENDIX 1. VISIT WINDOWS

These windows are intended for data summaries by time point. When multiple assessments fall within a window, the assessment closest to the nominal time will be used in summaries. If there are multiple visits equally distant from the midpoint of a window, then the earlier visit will be used.

Efficacy Assessments

No	End Point	From Imaging Dose 1	From Therapeutic Dose 1	From Therapeutic Dose 2
1	Overall Tumor Response (CT/MRI Scans)	Screening / Baseline (Day -28 to Day 0)	Month 3 (Day 81 - Day 101) Month 6 (Day 173 - Day 193) Month 9 (Day 264 - Day 284) Month 12 (Day 355 - Day 375) Month 18 (Day 518 - Day 578) Month 24 (Day 700 - Day 760) Month 30 (Day 883 - Day 943) Month 36 (Day 1065 - Day 1125) Month 42 (Day 1248 - Day 1308) Month 48 (Day 1430 - Day 1490) Month 54 (Day 1613 - Day 1673) Month 60 (Day 1795 - Day 1855)	
2	Tumor Markers	Screening / Baseline (Day -28 to Day 0)	Week 2 (Day 8 - Day 14) Week 4 (Day 22 - Day 28) Week 6 (Day 36 - Day 42) Week 8 (Day 50 - Day 56) Week 10 (Day 64 - Day 70) Week 12 (Day 78 - Day 84) Week 14 (Day 92 - Day 98) Week 16 (Day 106 - Day 112) Week 18 (Day 120 - Day 126) Week 20 (Day 134 - Day 140) Week 22 (Day 148 - Day 154) Week 24 (Day 162 - Day 168) Month 7 (Day 203 - Day 223)	

No	End Point	From Imaging Dose 1	From Therapeutic Dose 1	From Therapeutic Dose 2
			Month 8 (Day 233 - Day 253) Month 9 (Day 264 - Day 284) Month 10 (Day 294 - Day 314) Month 11 (Day 325 - Day 345) Month 12 (Day 355 - Day 375) Month 18 (Day 518 - Day 578) Month 24 (Day 700 - Day 760) Month 30 (Day 883 - Day 943) Month 36 (Day 1065 - Day 1125) Month 42 (Day 1248 - Day 1308) Month 48 (Day 1430 - Day 1490) Month 54 (Day 1613 - Day 1673) Month 60 (Day 1795 - Day 1855)	
3	Soloway Score (Bone Scan) and optional FDG-PET Scan	Screening / Baseline (Day -28 to Day 0)	Month 3 (Day 81 - Day 101) Month 6 (Day 173 - Day 193) Month 9 (Day 264 - Day 284) Month 12 (Day 355 - Day 375)	
4	Karnofsky Performance	Screening / Baseline (Day -28 to Day 0)	Day 1 Week 6 ± 10 days (Day 32 - Day 52) Month 3 (Day 81 - Day 101) Month 6 (Day 173 - Day 193) Month 9 (Day 264 - Day 284) Month 12 (Day 355 - Day 375)	Day 1 Week 6 ± 10 days (Day 32 - Day 52)

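### SAP 7.4.7 confirms a tumor-marker response at the next draw, usually about two weeks later, where the protocol requires at least four weeks, and the departure is not recorded

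*SAP*

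**What the plan says.** Protocol 13.3.2.2.2 (Tumor Marker Response Proportion) defines CR and PR for each marker. It then states that the change "must be confirmed by repeat assessments that should be performed no less than 4 weeks after the criteria for response are" first met.

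SAP 7.4.7 (Tumor Markers) uses near-identical response categories, but its footnote stops short of the interval: "To be assigned a status of CR or PR changes in tumor marker measurements must be confirmed by repeat assessments". The text below the table supplies the working rule: "A confirmed response will require that the subsequent tumor marker assessment be identical or better compared with the previous response assessment". No minimum interval appears in that section. For RECIST response, SAP 7.4.5 keeps a four-week minimum.

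The sampling schedule is in Protocol 9.1: "every two weeks for the first 24 weeks after the first Therapeutic Dose starting at Week 2, and monthly during months 7-12". Protocol 11.5.10 agrees ("measurements every two weeks during weeks 2-24"), and SAP Appendix 1 gives the matching visit windows.

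Protocol 13.5 says that changes from the protocol's analysis will be documented in the final SAP. The entry for 7.4.7 in SAP section 9 mentions a clarification of the marker analyses, a change in correlation measures and an added binary comparison. It does not mention the confirmation interval.

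**The concern.** A confirmation interval is meant to separate a durable fall from a brief one. With two-weekly sampling, next-draw confirmation lets two adjacent low values count as a confirmed response. Protocol 7.4 describes catecholamine secretion as episodic and measurement of the parent compounds as variable, so a low stretch of about two weeks is plausible for those markers.

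Confirmed marker response is used in several places in SAP 7.4.7:

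- best confirmed response per marker and its duration;
- the overall marker responder, which requires CR or PR on every plasma and urine marker abnormal at baseline except urine VMA;
- the association with primary-endpoint status;
- the cross-tabulation with RECIST response, which would set a marker response confirmed at about two weeks against a tumor response confirmed at four weeks or more.

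**Working it through.** The documents state no rate, sample size or power for marker response, so there is no figure to reproduce. The check has three parts.

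**1. Gaps between scheduled draws.** The inputs are the SAP Appendix 1 windows. The smallest gap is the start of the later window minus the end of the earlier one. The largest is the end of the later window minus the start of the earlier one.

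- Two-weekly draws, for example "Week 2 (Day 8 - Day 14) Week 4 (Day 22 - Day 28"): smallest 22 − 14 = 8 days, largest 28 − 8 = 20 days, nominal 14 days.
- Week 24 (Days 162–168) to Month 7 (Days 203–223): smallest 203 − 168 = 35, largest 223 − 162 = 61, nominal 213 − 165 = 48 days.
- Monthly draws, for example "Month 8 (Day 233 - Day 253) Month 9 (Day 264 - Day 284"): smallest 264 − 253 = 11, largest 284 − 233 = 51. Across the five monthly pairs the range is 10 to 51 days, nominal 30 or 31.

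There are 12 two-weekly and 6 monthly draws, so 18 draws and 17 adjacent pairs. Eleven pairs (11/17 = 65%) are two-weekly, and none of these can reach 28 days unless a draw is missed or out of window. In Months 7 to 12 the next draw is nominally late enough, but the windows do not guarantee it.

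**2. The two rules on fixed patterns.**

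- Criteria met at Weeks 4 and 6 only: confirmed under the SAP, because the next draw is no worse. Not confirmed under the protocol, because no qualifying draw lies 28 days on.
- Criteria met at Weeks 4 and 8 but not Week 6: not confirmed under the SAP, because the next draw is worse. Confirmed under the protocol if any qualifying draw at least 28 days later is enough.

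The rules therefore differ in both directions. The protocol does not say which of these it means: (A) any qualifying draw at least 28 days later; (B) the first draw at least 28 days later; (C) every draw across at least 28 days.

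**3. Illustrative size.** The documents give no marker variability, so these inputs are assumptions: a log-normal marker, within-subject log-SD of 0.20 to 0.50, serial correlation decaying with a time constant of 20 days, a measured baseline carrying the same noise, and response meaning a fall of at least 50% at the 18 window midpoints. Percent of subjects confirmed:

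| Scenario | SAP next draw | A | B | C |
|---|---|---|---|---|
| No true change, log-SD 0.20 | 1.5 | 2.0 | 1.0 | 0.8 |
| No true change, log-SD 0.35 | 18.8 | 24.4 | 15.5 | 13.1 |
| No true change, log-SD 0.50 | 35.8 | 43.9 | 31.6 | 27.7 |
| Temporary 45% fall, about Weeks 4–10, log-SD 0.20 | 31.9 | 24.1 | 23.2 | 19.5 |
| Sustained 60% fall, log-SD 0.20 | 95.7 | 97.6 | 94.7 | 93.7 |

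For a yes/no response, the SAP count cannot fall below C, because a response held at every draw is also held at the next one. Against B it was equal or higher, within simulation error, for correlation times of 0, 20 and 60 days. Against A it was lower in most settings and higher mainly for a short dip. The model ignores normalization and a slip from CR to PR, which the SAP's wording would not count as identical or better.

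**The case against.** The strongest reply concerns direction. A reader might infer that the SAP rule inflates the confirmed response rate. The documents do not support that as a fact. The SAP rule is shorter, but in one respect stricter: a single worse value at the next draw blocks that confirmation. Under reading A, which the protocol's wording does not exclude, the SAP gives fewer confirmed responders in most of the settings tried. This part of the objection stands.

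Three further points stand in part.

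- Protocol 7.4 says metanephrines are produced continuously and independently of catecholamine release. The episodic-secretion argument therefore bears mainly on the catecholamines, not on the whole panel.
- SAP section 9 tracks changes from SAP Version 1.0, which is not available here, so it cannot show when the interval was dropped. Protocol 13.5 still requires a departure from the protocol to be documented in the final SAP, and it is not.
- SAP 7.4.7 lists all marker values and the duration of each response, so brief responses can be found in the listings. They would still be counted as confirmed in the summary tables.

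It could also be said that the protocol sentence speaks of tumor measurements and was carried over from the RECIST text. However, it sits in the marker section directly after the marker criteria. The SAP footnote repeats the requirement for marker measurements, with the interval missing.

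**Conclusion.** The conflict holds. Through Week 22, confirmation at the next in-window draw comes 8 to 20 days later and never meets the protocol's four-week minimum. The SAP can confirm short-lived decreases that the protocol would not, so its marker response is not the protocol's secondary endpoint. That conclusion needs only the two texts and the visit windows.

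The effect on the reported rate is not established in direction or size. If response must hold throughout the four weeks, the SAP count is equal or higher. If it must hold at the first draw at least 28 days on, the illustrations show the SAP rate equal or higher. If any later qualifying draw suffices, it can be lower. Every percentage above rests on assumed variability and correlation. With a large sustained fall the rules nearly agree (93.7% to 97.6%).

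The concern is strongest for the catecholamines. It affects a secondary endpoint that has no success criterion and leaves the primary test untouched.

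**What to change.** In SAP 7.4.7, require at least 28 days between first meeting the CR or PR criteria and the confirming assessment, as Protocol 13.3.2.2.2 does. State explicitly how intermediate assessments count. One option is that response must hold at the first assessment at least 28 days later. This is a choice to be declared, since the protocol does not specify it, and so would be a requirement that all draws in between also qualify.

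If next-draw confirmation is kept, document it in the SAP as a change from the protocol, with a reason, and report the 4-week definition alongside it.

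The cost is SAP wording and minor reprogramming, with no new data. The reported marker response rate may be lower.

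### SAP 7.4.7 counts markers abnormal at baseline in the overall marker-responder rule but gives no response to markers below 1.5 x ULN, so on a literal reading a mildly raised plasma or urine marker (other than VMA) rules out overall response

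*SAP*

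**What the plan says.** All the relevant text is in SAP 7.4.7, Tumor Markers.

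- **Per-marker evaluability.** The opening paragraph begins an exclusion with "If the tumor marker value prior to dosing is less than 1.5 times the upper limit of normal" and ends it with "it will not be included in this analysis". The Not Evaluable row of the response table gives the same limit: "Below 1.5 X ULN at baseline, or baseline missing".
- **Where a best confirmed response exists.** "Subjects will be evaluated to determine the best confirmed response for each tumor marker that is ≥ 1.5 x ULN at baseline".
- **Overall responder.** "An overall responder will be a subject who achieves a best confirmed response of either CR or PR at some time point", and this must hold "on each of the plasma and urine tumor markers that were abnormal at baseline", urine VMA excepted.
- **Normal and abnormal.** The CR row treats a value at or below ULN as normalised. The section gives no other boundary and does not define abnormal.

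The section does not say what happens in the overall rule when a counted marker is Not Evaluable, or how to classify a subject with no counted marker. Protocol 13.3.2.2.2 contains neither the 1.5 x ULN limit nor an overall-responder rule, so it does not settle the question.

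**The concern.** The overall rule requires a response on every counted marker, so one counted marker that cannot be assigned a response decides the outcome. The counting criterion (abnormal) and the evaluability criterion (at least 1.5 x ULN) are stated separately and never linked. If they differ, markers between them are required to respond but are never assessed for response.

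Two programmers could follow this text and produce different responder counts from the same data. On the literal reading, the count would also be lowered by a mismatch of definitions rather than by lack of response. Tumor marker response is a listed secondary objective (SAP 4.3), and the overall responder is the only subject-level classification that combines all the plasma and urine markers.

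**Working it through.** The documents state no figure for the overall marker responder rate, so there is nothing to reproduce. The check is one of logic, followed by an illustration of exposure.

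**Step 1: status of one marker.** Let b be the baseline and x the best confirmed later value, both in multiples of ULN. The SAP 7.4.7 table gives:

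- b < 1.5: Not Evaluable, whatever x is
- b ≥ 1.5 and x ≤ 1.0: CR
- b ≥ 1.5 and 1.0 < x ≤ 0.5b: PR
- otherwise SD or PD

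**Step 2: the overall rule under two readings of abnormal.**

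| Baseline b (plasma or urine, not VMA) | A: abnormal means b > 1.0 | B: abnormal means b ≥ 1.5 |
|---|---|---|
| b ≤ 1.0 | not counted | not counted |
| 1.0 < b < 1.5 | counted, always Not Evaluable, rule fails | not counted |
| b ≥ 1.5 | counted, can be CR or PR | counted, can be CR or PR |

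The readings differ only in the middle row. A baseline of exactly 1.5 x ULN is evaluable under both.

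**Step 3: example subject with three counted markers.**

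- 4.0 to 0.8 x ULN: CR
- 6.0 to 2.0 x ULN: PR, since (6.0 − 2.0)/6.0 = 67% fall and the value is still above ULN
- 1.3 to 0.7 x ULN: Not Evaluable, although it normalised

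Reading A gives a non-responder; reading B gives a responder.

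**Step 4: direction.** Every marker counted under B is also counted under A. Among subjects with at least one evaluable counted marker, the responders under A are therefore a subset of those under B, and A cannot give the higher rate. If R is the rate under B and s is the share of those responders who also have a marker in the middle row, the rate under A is R(1 − s). The understatement is R × s.

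**Step 5: exposure, for illustration only.** Protocol 11.5.10 lists 2 plasma free metanephrines, 3 plasma catecholamines, 3 urinary catecholamines and 2 urinary metanephrines: 2 + 3 + 3 + 2 = 10 markers, leaving out urine VMA and serum chromogranin A. Let q be the chance that a given marker lies in the middle row. With m independent markers, the share of subjects with at least one is 1 − (1 − q)^m. Both q and independence are assumptions; neither is in the documents.

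| m | q = 2% | q = 5% | q = 10% | q = 20% |
|---|---|---|---|---|
| 3 | 5.9% | 14.3% | 27.1% | 48.8% |
| 5 | 9.6% | 22.6% | 41.0% | 67.2% |
| 10 | 18.3% | 40.1% | 65.1% | 89.3% |

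Marker values are probably correlated, which would generally lower these shares. The table shows who has such a marker, not how many lose responder status. A subject loses it only by also responding on every evaluable counted marker.

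**The case against.** The strongest reply is that the section, read in sequence, already resolves the conflict. Markers below 1.5 x ULN are excluded at the outset. The paragraph just before the overall rule derives a best confirmed response only at or above 1.5 x ULN, and the overall rule reuses the term best confirmed response. On that view, low markers simply drop out. This reading is possible, and because of it one cannot say that a mildly raised marker makes a subject a certain non-responder. It is not stated, however. The exclusion sentence introduces the per-marker table, and the overall rule switches to a different word immediately after a paragraph that used the numerical limit.

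A second reply is that abnormal need not mean above ULN. Protocol 12.2.1 defines an abnormal value as one outside the reference range, but it does so for local laboratory tests, and Protocol 11.5.10 has the markers measured centrally. That is fair: the definition supports the literal reading without settling it. The CR row of the marker table is the closer evidence.

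Third, not every marker is affected. Urine VMA is expressly excepted, and chromogranin A is a serum marker, so it is arguably outside a rule about plasma and urine. This limit stands.

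A reader might also infer that the planned association between marker response and primary-endpoint status is biased downward. The documents do not support that. SAP 7.4.7 words the association in terms of an overall best marker response of CR or PR and does not tie it explicitly to the all-markers responder. A lower responder rate would not by itself show bias in an association.

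**Conclusion.** The point holds as a conflict between two stated criteria within SAP 7.4.7. On the literal reading, a counted plasma or urine marker with a baseline above 1.0 and below 1.5 x ULN makes overall response impossible, and the overall responder rate is understated. On the alternative reading the problem disappears, but the SAP does not say that this reading applies.

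The size is unknown. A reader might take the exposure shares above to mean that a large fraction of subjects would be wrongly classed; they do not show this. They rest on an assumed q and on independence, and they only cap the loss, which is R × s with both terms unknown.

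The reach is limited to one derived summary of a secondary endpoint. The primary analysis, the sample size, the per-marker tables and the dominant-marker analysis do not use the overall rule, and the table list in SAP Section 11 names no table dedicated to it. The change is still worth making because the ambiguity alters responder counts and is easily removed.

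**What to change.** In the overall-responder rule of SAP 7.4.7, replace the condition that a marker be abnormal at baseline with the condition that it be at least 1.5 x ULN at baseline, keeping the urine VMA exception. This uses the limit that the section already applies to each marker.

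Add one sentence: subjects with no evaluable plasma or urine marker other than VMA are Not Evaluable for overall marker response and leave the denominator, and their number is reported. Without it, a subject whose counted markers all drop out could be taken either as meeting the rule by default or as failing it.

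The cost is one phrase, one sentence and a subject-level Not Evaluable category in the programming. No new data are needed. The SAP treats database lock as still to come, so the edit can be made beforehand. The downside is a smaller denominator for this one secondary summary, which reporting the excluded number makes visible.
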